8 STATISTICAL METHODS

8.1 General statistical conventions

All statistical procedures will be completed using SAS® version 9.3 or higher.

Unless otherwise stated, all statistical testing will be two-sided and will be performed using a significance (alpha) level of 0.05. Two-sided 95% confidence intervals (CI) will be provided for the difference between treatment groups.

Descriptive statistics (mean, standard deviation, 95% confidence interval for mean, minimum, median, maximum, and number of observations and missing cases) will be used for quantitative variables. Frequencies and percentages will be used for categorical variables. The summaries will be presented by treatment group, unless otherwise specified. Percentages will be rounded to one decimal place.

Unless stated otherwise, unscheduled data will not be included in the summaries or analysis.

8.2 Data Listing

All subject data will be presented in individual subject data listings. Unless otherwise stated, unscheduled visit results will be included in date/time chronological order, within subject listings only. All listings will be sorted by treatment group, investigational site, subject number, date/time and visit. Subject's gender and age will be stated on each listing. Unless otherwise stated, data listings will be based on all randomized subjects.

8.3 Subject disposition

All subjects who were screened as well as provided informed consent will be included in a summary of subject disposition. The number of subjects screened, the number of screen failures, the number of subjects with each reason for screen failure will be presented overall. All subjects will be included.

The number and percent of subjects randomized, re-consent to Protocol Amendment 1.2.11

(COVID-19 outbreak), took a dose of study drug, randomized and not treated, treated and not randomized will be presented. The number of subjects that discontinued prematurely by visit will be presented along with the primary reason for premature discontinuations including 'Withdraw due to the COVID-19 outbreak'. Also, the number of subjects that complete the M3, M6, M9, M6/M9 visits and completed the study will be summarized. All summaries will be provided by treatment group and overall.

The number and percent of subjects in each analysis population will be tabulated. The number of subjects randomized will be used as the denominator for the percentage calculation.

Randomization details and Subject disposition data will be listed.

The informed consent data including 'patient re-consent to Protocol Amendment 1.2.11 (COVID-19 outbreak)' will be provided in a listing.

The data of each visit including 'if the visit was modified due to COVID-19 outbreak' data will be provided in a listing.

8.4 Protocol deviations

All protocol deviations and major protocol deviations identified will be summarized by treatment group and overall.

All protocol deviations and major protocol deviations related to COVID-19 identified will be summarized by treatment group and overall.

A listing of all subjects with protocol deviations will be provided by treatment group, including flag for COVID-19 related protocol deviation. A separate listing of randomized subjects that violated inclusion/exclusion criteria will be provided.

8.5 Demographics and baseline characteristics

No formal comparison between treatment groups for demographic or baseline characteristics will be done. All demographic and baseline characteristics data will be listed.

8.5.1 Demographics

Age and other continuous demographic variables at baseline will be summarized using descriptive statistics (mean, standard deviation, median, minimum, maximum and number of missing cases for quantitative parameters and percentages and number of missing cases for the qualitative parameters) by treatment group and overall. Included will be Age category (\geq 65 to <75 years, \geq 75 years), gender, race, participation in SARA OBS study, country and region (EU/US) will be summarized using the FAS.

8.5.2 Baseline characteristics

The following continuous variables, at baseline, will be summarized by descriptive statistics for the FAS.

- Height,
- Weight,
- BMI,
- Calf circumference,
- Waist circumference,
- Hip circumference,
- Mid-arm circumference,
- Tricipital plica thickness,
- Gait speed during 400m walking test (m/sec),
- PF-10 score,
- Total score (including severity index/co-morbidity index) of Cumulative Illness Rating Scale (CIRS). Severity index = results from the average of the scores of the first 13 categories (excluding the category "psychiatric / behavioral pathologies"). Comorbidity index = the

number of categories in which a score higher than or equal to 3 is obtained (excluding the category "psychiatric / behavioral pathologies")

- By domain and total score of Pepper Assessment Tool for Disability (PAT-D),
- Physical and mental component summary of SF-36
- Score of Mini Nutritional Assessment short Form (SF-MNA). For derivation refer Appendix E.

8.5.3 Medical history

A summary (frequency and percentage) of medical history by treatment group and overall will be presented by system organ class (SOC) and preferred term (PT) using Medical Dictionary for Regulatory Activities (MedDRA) Version 21.0 or higher for the safety population. All medical history will be listed.

8.5.4 Prior and Concomitant medications

Medications used in this study will be coded by using the latest available version of the World Health Organization Drug Dictionary Enhanced (WHODDE).

Prior medications are defined as those medications with a start and end date prior to the first dose of study drug.

Concomitant medications are defined as those medications with a start date on or after the date of first dose of study drug. A medication which started prior to first dose and continued after first dose will also be considered as concomitant medications.

Prior and Concomitant medications will be summarized descriptively using frequency and percentage by Anatomical Main Group [1st level of the Anatomical Therapeutic Chemical (ATC) classification], and preferred name by treatment group using the safety population.

Subjects with multiple medications in the same ATC class or preferred name will be counted only once for that respective ATC class or preferred name.

Details for imputing missing or partial start and/or stop dates of medication are described in section 7.1.4

A listings of prior and concomitant medications will be provided.

8.6 Extent of exposure

8.6.1 Treatment duration

Study drug exposure (in days) will be summarized by treatment group for the safety population using descriptive statistics.

Exposure to study drug will be categorized in intervals (1-27 days, 28-83 days, 84-146 days, 147-

Version Final 2.0, Date: 04JUN2021

Page 28 of 69

181 days, 182-223 days, 224-272 days, \geq 273 days) and will be summarized by treatment group for the safety population.

8.6.2 Treatment compliance

Study drug compliance will be summarized by treatment group using descriptive statistics. The following compliance categories will be summarized "<80%" "80 - 100%" and ">100%" by frequency and percentage.

The summaries will use the safety population.

Study drug exposure and compliance data will be provided in a listing.

The data of study drug compliance at each visit will be provided in a listing.

8.7 Efficacy analyses

This section addresses separately the analyses to be conducted on the primary, key secondary and secondary efficacy endpoints.

Analyses for the primary and key secondary efficacy endpoints will be analyzed using the FAS and PP population. Analyses for all non-key secondary efficacy and exploratory endpoints will be analyzed using the FAS only.

The definition of efficacy endpoints is detailed in section 4.

Summary value and change from baseline of endpoints by visits will be summarized for Baseline, M3, M6, M9, M6/M9, including n, mean, median, standard deviation, minimum, maximum.

Analysis of Mixed Model for Repeated Measures (MMRM) will be provided for M3, M6/M9. M6/M9 data comes from M6, but M9 value will be used if M6 is missing.

Summary value and change from baseline of primary efficacy endpoint will be summarized for Last assessment on treatment. Last assessment on treatment is defined as the last non-missing value from the post-baseline treatment period.

8.7.1 Analysis methods

Treatment group comparison (175 mg BIO101 Vs Placebo and 350 mg BIO101 Vs Placebo) will be tested at a significance level of 0.05, 2-sided unless stated otherwise.

8.7.1.1 Analysis of Mixed Model for Repeated Measures (MMRM)

The analysis of the efficacy endpoints collected over time will use a MMRM analysis on change from baseline. An estimate of the contrast between each active arm and placebo (after adjusting for the Hochberg procedure, primary and key secondary endpoints only) at M6/M9 will be made. The MMRM model will include treatment, visit, center, gender (center and gender are stratification factors) as fixed effects, treatment*visit as interaction terms and baseline value as a covariate (if a

Version Final 2.0, Date: 04JUN2021

Page 29 of 69

baseline value for that endpoint is collected). An unstructured covariance matrix (there is no assumption of a particular correlation structure for repeated measurements within subjects over time) will be used to estimate the within-subject covariance. The denominator degrees of freedom will be calculated according to the Kenward-Roger method.

The Least-squares [LS] means, LS mean difference between each active arm and the placebo group (reference category), standard error, two-sided 95% CIs for the LS means and difference between treatment groups and p-value for treatment differences will be presented. The p-values for the effects will also be presented. The number of patients in the analysis population and number of patients in the analysis will be provided by treatment group.

The MMRM model will give a correct estimation in the presence of missing data, under the missing at random (MAR) assumption. This analysis will provide an estimate of the efficacy of 175mg bid BIO101 and 350mg bid BIO101 in the population who stay in the study until 6/9 months.

In case of non-convergence of the above model using an unstructured covariance matrix, the following variance structure will be used in this order: Heterogeneous Toeplitz, Toeplitz and Compound Symmetry. The final covariance structure used will be documented in the CSR.

Due to the quantitative form of the primary and key secondary endpoints (400MW gait speed, PF10 and handgrip strength test) and the large number of patients, the normal assumption for the residuals of the mixed models will be assumed.

The SAS code used to implement this analysis is given in Appendix A.

8.7.1.2 Analysis of covariance (ANCOVA) model for Change from Baseline

The analysis of the efficacy endpoints will use an ANCOVA on change from baseline to M6/M9. An ANCOVA on change from baseline to last assessment on treatment for primary endpoint will be performed.

The model will include treatment, center and gender (center and gender are stratification factors) as fixed effects and the baseline measurement as a covariate.

The model will be used to derive least squares estimates of the treatment differences (each active arm versus placebo) in mean change and two-sided 95% confidence intervals. Also t-statistics corresponding to the type III sums of squares for the differences in the least squares means will be used to obtain p-values for treatment group comparisons (each active arm versus placebo group). The LS means and associated two-sided 95% CIs for the mean change within each treatment group will be calculated. The p-values for the effects will also be presented. The number of patients in the analysis population and number of patients in the analysis will be provided by treatment group.

Due to the quantitative form of the endpoints (400MW gait speed, PF10 and handgrip strength test) and the large number of patients, the normal assumption for the residuals of the mixed models will

be assumed.

8.7.1.3 Logistic Regression

Analysis of response data (responder/non-responder) at M6/M9 will use a logistic regression model. Analysis of response data at last assessment on treatment for primary endpoint will use a logistic regression model.

The model will include treatment, center and gender as fixed effects and baseline score as a covariate.

The multiplicity issue due to the two doses of active treatment will be addressed using the Hochberg procedure.

The number of subjects in the analysis population, number of subjects in the analysis, odds ratio (OR), two-sided Wald 95% CIs and p-value based on Wald chi-square test for 175 mg BIO101 Vs Placebo and 350 mg BIO101 versus placebo will be presented.

The SAS code used to implement this test is given in Appendix A.

8.7.1.4 Cochran Mantel-Haenszel (CMH) Test

Analysis of success rate or risk ratio will use a CMH test with center and gender as stratification (adjustment) variables.

The adjusted relative risk (adjusted for center and gender) based on the ratio of success rates for each treatment group versus placebo, 95% CI for the adjusted relative risk and CMH p-value will be presented.

The SAS code used to implement this test is given in Appendix A.

8.7.1.5 Pearson Correlation co-efficient

In order to the strength and direction of the linear relationship between the two variables, a Pearson correlation co-efficient along with the p-value will be presented.

The SAS code used to implement this test is given in Appendix A.

8.7.1.6 Multiplicity

To strictly control overall type I error rate for the analysis of the primary and the key secondary endpoints to a two-sided 5% level, a Hochberg procedure will be used.

The aim of the study is to show that at least one dose is statistically superior to placebo while the family-wise type I error rate is maintained at the two-sided $\alpha = 0.5$ for the following primary and key secondary endpoints.

- Change from baseline to month 6 (M6)/ month 9 (M9) in 400MW gait speed
- Change from baseline to M6/M9 in Physical Function Domain (PF-10) sub-score of the Short Form Health Survey (SF-36)
- Change from baseline to M6/M9 in Handgrip strength test

The null hypotheses H_{01} and H_{02} given below will be tested against the alternative hypotheses H_{A1} and H_{A2} associated with the 175 mg BIO101 and 350 mg BIO101 groups respectively:

Where μ_1 and μ_2 denote the mean change from baseline at M6/M9 in the 175 mg BIO101 and 350 mg BIO101 groups. With μ_p denoting the mean change from baseline at M6/M9 in the placebo group.

A statistical rejection of H_{01} (or H_{02}) will indicate that the 175 mg BIO101 (or 350 mg BIO101) is superior to placebo or we say that the 175 mg BIO101 (or 350 mg BIO101) is significantly better than placebo. When at least one dose is significantly better than placebo, we say that the study is positive.

Two-sided p-values for comparing the 175 mg BIO101 to placebo and comparing the 350 mg BIO101 to placebo are denoted by p_{01} and p_{02} , respectively. The first step is to compare max (p_{01} , p_{02}) to 0.05. If max (p_{01} , p_{02}) \leq 0.05, both doses are claimed to be statistically better than placebo. If max (p_{01} , p_{02})> 0.05, the second step is needed to compare min (p_{01} , p_{02}) to 0.5/2 =0.025. If min (p_{01} , p_{02}) \leq 0.025 at the second step, the dose with is concluded to be statistically better than placebo. Otherwise no dose can be claimed to be better than placebo.

Multiplicity concerns for the non-key secondary endpoints are kept under control by the prespecification of key-secondary endpoints and a low number of secondary endpoints and analyses. Analysis of the non-key secondary endpoints will be considered supportive and no adjustments for multiplicity will be made.

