9 STATISTICAL CONSIDERATIONS

9.1 STATISTICAL HYPOTHESES

The main hypothesis to be tested in this study is the superiority of at least one dose of active versus placebo on the change from baseline of the 400 m gait speed criterion after 6 months of treatment.

In order to deal with the multiplicity issue due to the two doses, a Hochberg procedure will be used for testing the main hypothesis.

Full details of the analysis and the procedure will be given in the statistical analyses plan (SAP) of the study.

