9.4 STATISTICAL ANALYSES

9.4.1 GENERAL APPROACH

The SAP will be finalized & signed-off before database lock and unblinding.

All inferential tests will be two-tailed and with a 5% alpha risk, unless otherwise specified.

Descriptive statistics (mean, standard deviation, 95% confidence interval for mean, minimum, median, maximum, and number of observations and missing cases) will be used for quantitative variables, and frequencies and percentages will be used for categorical variables. The descriptions will be broken down by treatment group.

A Hochberg procedure will be used to deal with the multiplicity concern on the main endpoint and the key secondary endpoints. Other multiplicity concerns (relative to secondary endpoints) are kept under control by the pre-specification of key-secondary endpoints and a low number of secondary endpoints and analyses.

Due to the quantitative form of the endpoints (gait speed PF10 and handgrip strength test) and the large number of patients, the normal assumption for the residuals of the mixed models will be assumed. However, if found necessary, additional non-parametric approach could be added and detailed in the SAP of the study.

The covariates included in the models are the stratification factors (gender and center) and the baseline score of the parameter if available. No interactions will be included by default in the models, however, in case of interesting findings in the subgroup analyses, further analyses would be conducted.

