9.4.3 ANALYSIS OF THE SECONDARY ENDPOINT(S)

The key secondary endpoints (handgrip strength and PF-10 sub-score of the SF-36) will be analyzed with the same strategy as the primary endpoint (i.e. using a repeated measures mixed model to estimate the contrast at M6 of the difference of each active group versus placebo).

Missing data will not be replaced in these analyses but the MMRM model on observed data is known to perform well under a MAR hypothesis.

Additional sensitivity analyses may be added in the SAP during the blind-review meeting if the number of missing data is important (more than 10%).

Concerning the responder endpoints:

- 1. for the PF-10 sub-score of the SF-36, a responder analysis will be performed with a responder definition of "patient with an improvement of PF-10 greater or equal to 2 points versus baseline", at an individual level.
- 2. for the handgrip strength test: a responder definition is equal to the minimal significant benefit set at least 2 kg of improvement versus baseline, at an individual level.

The rate of responders (according to the predefined definitions provided in the corresponding endpoint sections) will be provided in each group of treatment at M3 and M6 visits for the PF-10 sub-score and at the M6 visit only for the handgrip strength test. Participants without any assessment for a parameter at a visit will be considered as non-responder for the corresponding parameter.

A logistic regression model with treatment group, gender and center as fixed effects will be used to compare each active group versus placebo at M6. The odds-ratio comparing groups will be provided as well as its 95% confidence interval. The multiplicity issue due to the two doses of active treatment will be addressed using the Hochberg procedure.

The other secondary and exploratory endpoints will be analyzed only in the FAS population.

Details and exploratory endpoints analyses will be provided in the SAP.

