8.7.2 Analysis of primary efficacy endpoint

The 400MW test used to calculate the 400MW gait speed will be performed at Screening, M3, M6/M9 and last assessment on treatment visits. The Screening value will be considered to be the baseline value. If the screening value is missing the baseline value will be considered as missing.

The main analysis of the primary endpoint (change from baseline to month 6 (M6)/month 9 (M9) in 400MW gait speed) will be performed using the FAS.

Change from baseline to M6/M9 in 400WM gait speed will be summarized by treatment group.

The main hypothesis to be tested in this study is the superiority of at least one dose of active versus placebo on the change from baseline in 400m gait speed after 6 months of treatment.

The null hypotheses H_{01} and H_{02} given below will be tested against the alternative hypotheses H_{A1} and H_{A2} respectively:

$$\begin{split} &H_{01}\!\!:\ \mu_1 - \mu_P \!<\! 0.1, \qquad H_{02}\!\!:\ \mu_2 - \mu_P \!<\! 0.1, \\ &H_{A1}\!\!:\ \mu_1 - \mu_P \geqslant 0.1, \qquad H_{A2}\!\!:\ \mu_2 - \mu_P \geqslant 0.1, \end{split}$$

Where μ_1 and μ_2 denote the mean change from baseline in meters per second in the 400MW gait speed at M6/M9 in the 175 mg BIO101 and 350 mg BIO101 groups. With μ_p denoting the mean change from baseline at M6/M9 in the placebo group. A minimum clinically significant benefit is set at 0.1 meter per second in the mean difference between groups (i.e., superiority margin).

A Mixed Effect Model Repeat Measurement (MMRM) model with fixed factors treatment and center and the baseline score and the stratification factor (gender) will produce an estimate of the contrast at M6/M9 in the change from baseline of the 400MW test gait speed between each active arm and the placebo group (section 8.7.1.1) (after adjustment by the Hochberg procedure (Section 8.7.1.6)).

The same MMRM model will be also fitted for the Per-Protocol population to give an estimand of the efficacy of 175mg BIO101 and 350mg BIO101 in the population with a good compliance to the protocol. The FAS is the main population/set of interest.

A by-subject listing of 400MW data will be provided.

Alternative methods to adjudicate missing data for the primary endpoint like the Bayesian Multiple Imputation (MI) methods will also be considered. Chen at al (2017) demonstrated the interest of applying Bayesian MI method to 400MW non-completers in the LIFE study⁹. More detail please refer to section 8.7.6.

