Appendix C.

The handgrip strength test will be performed at Day 0 and at the M6/M9 visit or the end-ofintervention visit and will be measured 3 times for both hands. Grip strength is considered as the dominant hand so the highest of all 3 attempts for the dominant hand will be used for the analysis. The highest value for each hand will be summarized by treatment group. If there has been current flare-up of pain or has undergone fusion, arthroplasty, tendon repair, synovectomy, or other related surgery for the dominant hand or wrist in the past 3 months, the other hand will be tested. For the handgrip strength test, a minimum clinically significant benefit is set at 2 kg difference in the change at M6/M9 from baseline versus placebo in the mean difference between treatment groups.

Fatigue strength will be summarized by treatment group.

The analysis of change from baseline to M6/M9 in Physical Function Domain (PF-10) will use the same method as for analysis of the primary efficacy endpoint as detailed in section 8.7.1.1.

Missing data will not be replaced in these analyses but the MMRM model on observed data is known to perform well under a MAR hypothesis.

An ANCOVA method detailed in section 8.7.1.12 will be used to analyse change from baseline to M6/M9 in Handgrip strength test.

Alternative methods to adjudicate missing data for the primary endpoint like the Bayesian Multiple Imputation (MI) methods will also be considered for Physical Function Domain (PF-10). Chen at al (2017) demonstrated the interest of applying Bayesian MI method to 400MW non-completers in the LIFE study⁹. More detail please refer to section 8.7.6.

A responder analysis will be performed, using a logistic regression (method defined in section 8.7.1.33) to model PF-10 response at M6/M9. A responder is defined as an improvement of PF-10 greater or equal to 2 points compared to the baseline value, at an individual level. A non-responder for a visit (M3 or M6/M9) will be defined as a subject that is not a responder at that visit. Subjects with a missing value at a visit (M3 or M6/M9) will be considered as non-responders. The number and rate (%) of responders and non-responders will be provided by treatment group for the M3 and M6/M9 visits.

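### SAP 8.7.1.6 promises 5% family-wise control over gait speed, PF-10 and handgrip, but the only steps it writes are a two-p-value Hochberg over the two doses

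*SAP*

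**What the plan says.** **The promise.** SAP 8.7.1.6 gives the aim as "To strictly control overall type I error rate for the analysis of the primary and the key secondary endpoints to a two-sided 5% level" and lists the change from baseline in gait speed, PF-10 and handgrip as the family.

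**The steps.** The same section defines two two-sided p-values, one per dose. The larger is compared with 0.05 and, if that fails, the smaller with 0.025. No endpoint index appears. It then says "When at least one dose is significantly better than placebo, we say that the study is positive" without naming an endpoint. Alpha is printed as 0.5 and the second threshold as 0.5/2; the working values 0.05 and 0.025 are printed correctly.

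**What points to control across endpoints.** Protocol 9.4.1: "A Hochberg procedure will be used to deal with the multiplicity concern on the main endpoint and the key secondary endpoints". It gives no steps.

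**What points to the two-dose rule, endpoint by endpoint.**
- Protocol 9.1: "In order to deal with the multiplicity issue due to the two doses, a Hochberg procedure will be used for testing the main hypothesis". Details are left to the SAP.
- SAP 8.7.1.1 attaches the adjustment to each active-versus-placebo contrast: "after adjusting for the Hochberg procedure, primary and key secondary endpoints only". SAP 8.7.3.1 sends PF-10 to that section, saying its analysis "will use the same method as for analysis of the primary efficacy endpoint".
- SAP 8.7.1.3 and the responder paragraphs of Protocol 9.4.3 use Hochberg in the responder analyses explicitly because there are two doses.

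**The main hypothesis.** SAP 8.7.2 puts it as "superiority of at least one dose of active versus placebo on the change from baseline in 400m gait speed".

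**The concern.** Three endpoints and two doses make six tests, and the written algorithm handles two of them. It controls the error for one endpoint. Neither document says how it extends to three. Two statisticians following this SAP could reach different PF-10 or handgrip conclusions from the same data. If the pair rule is simply run three times, a significant key secondary result is weaker evidence than the promise of strict control implies. The SAP classes its other secondary endpoints as supportive and unadjusted, so a reader will take PF-10 and handgrip as protected.

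**Working it through.** **Inputs.** From the documents: two-sided 5% and thresholds 0.05 and 0.025 (SAP 8.7.1.6); 1:1:1 allocation (SAP 3.1), so the two dose contrasts share the placebo arm and correlate at 0.5. Assumed: a common between-endpoint correlation, which neither document gives, varied from 0 to 0.9; true differences of zero; fixed sample size; normal approximation.

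**Step 1: the stated 5% on one endpoint.** With c1 = 1.960 and c2 = 2.241 (two-sided 0.05 and 0.025),

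P(any false claim) = 1 − P(|Z1| < c2, |Z2| < c2) + P(c1 < |Z1| < c2, c1 < |Z2| < c2).

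At correlation 0.5 this is 4.80% (5.00% if the contrasts were independent). The written steps therefore meet the 5% for gait speed alone; the share in the drug's favour is 2.4%.

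**Step 2: the same steps repeated on each endpoint.** For independent endpoints, PF-10 or handgrip gives 1 − (1 − 0.048)² = 9.4%, and all three give 1 − (1 − 0.048)³ = 13.7%. Simulation with 2,000,000 trials per setting, three arms and a shared placebo gives the rest. The figure in brackets counts only claims in the drug's favour.

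| Assumed correlation | False PF-10 or handgrip claim | Any false claim, three endpoints | One Hochberg over six p-values |
|---|---|---|---|
| 0 | 9.3% (4.7%) | 13.7% (7.0%) | 4.7% |
| 0.3 | 9.2% (4.6%) | 13.2% (6.6%) | 4.6% |
| 0.5 | 8.8% (4.4%) | 12.2% (6.1%) | 4.3% |
| 0.7 | 8.1% (4.1%) | 10.7% (5.4%) | 3.8% |
| 0.9 | 6.8% (3.4%) | 8.2% (4.1%) | 3.0% |

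The third column includes the controlled gait-speed error. The second does not depend on whether gait speed truly improves.

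**Step 3: the other reading.** The last column shows that one Hochberg over all six p-values would keep the promise. It is not what is printed. Its strictest threshold is 0.05/6 = 0.0083, and two gait-speed p-values at or below 0.05 would no longer be enough by themselves.

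**Step 4: what the readings cost on gait speed.** With Protocol 9.2 inputs (0.1 m/s, SD 0.20, 64 per group) the noncentrality is 0.1 / (0.20 × √(2/64)) = 2.83. Power for at least one dose is:
- printed pair rule: 86.9% if both doses work, 73.3% if one works;
- Hochberg over six: 74% and 58%, assuming no key secondary effect.

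The choice of reading therefore matters for the primary test as well.

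**The case against.** **The inflation is conditional.** The opening of SAP 8.7.1.6 and Protocol 9.4.1 both speak of control across endpoints. If a six-way Hochberg was meant, nothing is inflated. This stands: the certain defect is that the written rule does not deliver the stated control, and the percentages belong to one reading of it.

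**Some apparent support for that reading is weak.** Protocol 9.4.3 says the key secondaries "will be analyzed with the same strategy as the primary endpoint", but the bracket that follows defines this as the mixed model, so it says nothing about multiplicity. The bracket in SAP 8.7.1.1, taken alone, fits either reading. Handgrip is sent to the ANCOVA in SAP 8.7.1.2, which does not mention Hochberg. These points stand too. The reading rests on Protocol 9.1, on SAP 8.7.1.1 read with the PF-10 text in 8.7.3.1, and on the responder text.

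**Practical weight is limited in phase 2.** About half of the two-sided excess favours placebo and cannot support a superiority claim. That is so, and the favourable-only rates are shown for this reason. But the SAP chose to promise strict two-sided control, so it should deliver that or withdraw it.

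**Stronger readings the documents do not support.** A reader might infer that the gait-speed result itself carries an 8 to 14% error, or that a PF-10 or handgrip result alone would make the trial positive. Protocol 9.1 and SAP 8.7.2 tie the main hypothesis to gait speed, and its pair rule is controlled. The positive-study sentence is loosely worded rather than a rule that any endpoint suffices.

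**Conclusion.** The point holds as a mismatch between a stated property and the written rule, and it should be fixed. Under the per-endpoint reading the excess over 5% appears at every correlation tried: about 7 to 9% for a false PF-10 or handgrip claim and about 8 to 14% for the named family, two-sided.

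The reassurance on gait speed (about 4.8%) has limits of its own. It is for a null of zero, whereas SAP 8.7.2 prints the gait-speed nulls as a difference below 0.1 m/s. It also leaves out any effect of the sample-size reassessment in Protocol 9.4.7, whose details the SAP defers to a separate interim analysis plan.

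**What to change.** Before unblinding, revise SAP 8.7.1.6 as follows.

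1. State that the 5% family-wise claim and the positive-study rule apply to the two-dose gait-speed comparison, and keep that Hochberg rule unchanged.
2. Report PF-10 and handgrip as supportive, with nominal p-values.
3. Enter this in the SAP's list of changes to the planned analysis, because it departs from Protocol 9.4.1.
4. Correct alpha from 0.5 to 0.05, and 0.5/2 to 0.05/2.

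The gait-speed test is unaffected. The cost is giving up confirmatory key secondary claims.

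If such claims are wanted, write out instead one procedure that controls the error over all six tests. The choice, and any order of PF-10 and handgrip, is the sponsor's. Three examples, with costs at 64 evaluable per group:

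- **Fixed endpoint order, moving on only if both doses pass.** Gait speed is unchanged, but the gate opens in about 70% if both doses work and about 3% if only one does.
- **A separate sequence for each dose at 0.025.** An effective dose reaches its first key secondary in about 72%. At-least-one-dose gait-speed power falls from 86.9% to 85.9% (both work) or from 73.3% to 73.1% (one works). The chance that both doses succeed falls from about 70% to 2 × 72.1% − 85.9% = 58%.
- **One Hochberg over six p-values.** It replaces the printed gait-speed thresholds, at the power cost shown in step 4.

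These are best-case figures. With 231 randomised and 20% lost, 231/3 × 0.8 = 61.6 per group remain, and the pair rule's 86.9% and 70% become about 85.6% and 68%. Protocol 9.2 expects losses above 20%.
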